#### **COVID-19 Protocol**

Starting Friday, 3/13/2020, all in-person meetings (including meeting between HEARS Staff and Clients and meetings between Teachers and Clients) have been paused due to COVID-19.

Teachers have been counseled to do all of their troubleshooting over the phone and to postpone all inperson visits until the end of COVID-19 stay-at-home order is lifted. If any Client needs a device replacement, a staff member will arrange a no-contact drop off with the client and a Teacher can help the client set up the device if they have any questions. The HEARS Trainer is also available to help with phone troubleshooting if needed.

In-person data collection will not permitted and all check-ins will be done via phone. All clients will outstanding primary outcome visits will be prioritized for HHIE collected via phone. HEARS staff will call clients for phone check-ins at their scheduled time to check in on the client and see if they are having any trouble with their device. For clients scheduled for a phone-check in, HEARS staff will attempt to get in touch 3 times through the client's primary number and then use all secondary contact methods (email, second number, emergency contact) at least once to reach the client. For clients who are due for their in-person visit, all contact attempts are the same as phone check-in attempts with the additional attempt to contact their service coordinator to assist with delivering a memo (if they are willing).

If a client brings up any concerns about COVID-19 or wants to know more resources, a "COVID-19 Resource guide" is available for study staff to reference some reminders and numbers that could be helpful to HEARS Clients.

For clients due for an in-person survey visit, staff will first collect a phone HHIE and then discuss options for collecting the rest of their answers to the HEARS Surveys (Following the COVID-19 Screening script). The screening script will address common limitations including limited cell phone minutes, internet connection, and comfort level with using technology. These methods are listed in order of study investigator preference for fidelity of data collection:

- 1. Zoom (with screen-share)
- 2. Skype (with screen-share)
- 3. Facetime or other video program (Hangouts, Duo, Facebook, etc)
- 4. Phone call with survey printout (printout mailed or delivered to them contact-free)
- 5. Phone call without survey printout

If a client is willing and able to complete additional surveys, a time will be scheduled where a HEARS Staff member will ask and collect their answers virtually.

Virtual surveys will be conducted in the order listed in Section 3 (same as in-person visits) other than if a client indicates they are not interested in completing the entire set of surveys.

Surveys will be prioritized in this order and as many as they are willing to complete will be completed (including offering to split up the meetings):

- 1. HHIE
- 2. UCLA
- 3. PHQ9
- 4. IOI-AI
- 5. Device Use
- 6. Program Evaluation
- 7. SF-12
- 8. SNI
- 9. VOL
- 10. Tech-SE
- 11. HEARS Basic Assessment
- 12. LSEQ
- b. Study duration and number of study visits required of research participants.

The study will take place over approximately 18 months. Details are summarized in Figure 4.

[figure not shown]

Figure 4: Overall Study Design and Timeline

An information session with a follow-up hearing screening will require an estimated total of 90 minutes. The meeting will introduce the study and HEARS program to interested participants, and screen consenting participants for study eligibility. Information sessions will be delivered by trained CHW's and the study staff.

Following attendance at an information session, study staff will meet with interested residents to obtain oral screening consent to undergo hearing screening and to gather other screening measures related to eligibility criteria. The participant will be advised about his/her eligibility. If eligible participants are interested in proceeding, the study staff will review the study, the associated written consent form, and obtain written consent. Participants will then complete baseline measurements and be randomized into either the immediate or delayed treatment groups. The baseline questionnaires will take approximately 45-50 minutes to complete.

Participants assigned to the immediate treatment group will be assigned a CHW. Once assigned to a CHW, the participant will meet with his/her assigned CHW to complete the intervention. The intervention will take place over two sessions and will take a total of approximately 120-150 minutes across two separate meetings. Follow-up evaluations at 1-week, 1-month, 2-months, 6-months, and 9-months post-intervention will be conducted via phone and will take approximately 10-15 minutes. Follow-up evaluations at 3-months and 12-months post-intervention will be conducted in-person by study staff with the participants and will take approximately 90 minutes per visit. In total, participants in the immediate treatment group will have contact with Baltimore HEARS study staff and CHW a minimum of 10 times. (see Figure 4 for overall study flow)

Participants assigned to the delayed treatment group will receive a call from study staff 1- and 2months following their baseline visit. They will then be scheduled for a 3-month repeat baseline visit with study staff that will take approximately 90 minutes. Following this visit, participants will be assigned a CHW and receive the intervention as outlined above. Follow-up evaluations at 1-week, 1-month, 2-months, 6months, and 9-months post-intervention will be conducted via phone and will take approximately 10-15 minutes. 3-month and 12-month post-intervention visits will be conducted in-person by study staff with the participants and will take approximately 90 minutes. In total, participants in the delayed treatment group will have contact with Baltimore HEARS study staff and CHW a minimum of 13 times (see Figure 4 for overall study flow). Of note, all participant visits, from the information session to follow-up visits, will be conducted at the participant's building.

c. Blinding, including justification for blinding or not blinding the trial, if applicable.

Study participants and data collectors will be unblinded as to randomization status. Participants will know which intervention group they are assigned to. Study staff collecting data will also be aware of group assignment depending on whether the participant is using the hearing device that is provided with the HEARS intervention. Study stuff analyzing trial data for the primary endpoint will be blinded to treatment group status.

d. Justification of why participants will not receive routine care or will have current therapy stopped.

Not applicable. There is no current standard of care for routine audiologic testing or hearing loss treatment in older adults. A recent United States Preventative Services Task Force report concluded that there was insufficient evidence to recommend screening or treatment for hearing loss in adults 50 years and older (Moyer, 2012).

e. Justification for inclusion of a placebo or non-treatment group.

All participants will receive the study intervention, either in the immediate group or the 3 month delayed treatment group.

f. Definition of treatment failure or participant removal criteria.

The intervention ("treatment") consists of aural rehabilitation, which includes basic education on agerelated hearing loss and communication strategies, and provision of an over-the-counter amplifier. The session will include fitting the device and a step-by-step orientation to the device. Treatments would be considered a failure if individuals do not complete the two-session intervention (i.e., did not attend all scheduled intervention meetings).

# g. Description of what happens to participants receiving therapy when study ends or if a participant's participation in the study ends prematurely.

After participants complete the intervention, they may continue to use the amplifier and communication strategies to their needs. Contact information for Sound World Solutions and Sonic Technology Products customer support, the device manufacturers, will also be provided and available to participants. We will also provide all participants with contact information for hearing care professionals who they can follow-up with if desired. The PI of the study is an otolaryngologist with expertise in hearing loss.

# 5. Inclusion/Exclusion Criteria

Participant inclusion criteria:

- Age 60 years or older
- English-speaking
- Aural-oral verbal communication as primary communication modality
- Post-lingual hearing loss (Audiometric pure tone averages [0.5-4kHz] in both ears >25 dB)
- Does not currently use a hearing amplification device or hearing aid
- Signed informed consent to participate in all study related activities
- Willing to regularly use listening device once provided for the remainder of their time in the study
- Hearing handicap as measured by HHIE-S score >8
- Able to follow study instructions

Recipient/participant Exclusion criteria:

- Individuals who do not fulfill inclusion criteria
- Evidence of ear disease or pathology requiring further medical evaluation

Participants are not required to have a communication partner, but they are encouraged to participate in the intervention with an individual they speak to regularly. For participants who have a communication partner, eligibility criteria is as follows:

Communication Partner Inclusion criteria:

- Age 18 years or older
- Speak to the participant on a daily basis
- English-speaking
- Aural-oral verbal communication as primary communication modality
- Able to accompany participant to all intervention sessions & study team meetings
- Able to follow study instructions

Communication Partner Exclusion criteria:

• Individuals who do not fulfill inclusion criteria

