### PARTICIPANTS

The study cohort will consist of older adults ( $\geq$  60 years old) with age-related hearing loss who are not currently utilizing a hearing aid or amplification device. Participants will be encouraged to involve a selfidentified communication partner willing to complete the program alongside them. Communication partners are any individuals with whom the participant engages in daily spoken communication.

A total of 175 participants will be recruited in partnership with Weinberg Senior Living and Catholic Charities, local nonprofit agencies that provide and oversee independent, subsidized housing buildings for low-to-moderate income older adults in Baltimore and local community sites. Weinberg Senior Living, which comprises ~ 1500 units of senior housing in 13+ buildings in the Baltimore area, has been our community partner in previous studies (IRB# NA\_00088278 and IRB# 00079481) and the current study (IRB#00152093).

[name], Director of Resident Services for Weinberg Senior Living, will assist the study team in communicating with building service coordinators and participant recruitment efforts. We will also work with Catholic Charities, which has 20+ building for senior living in the Baltimore metropolitan area. [name], Division Director for Senior Services of Catholic Charities, and his staff will assist the research team in recruiting participants and providing space for intervention delivery. Participants will also be recruited from other community sites (such as Baltimore City senior centers and social clubs) and independent senior living buildings in Baltimore City.

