### STUDY DESIGN

Initially, the study will be based in several buildings from Weinberg Senior Living and Catholic Charities in Baltimore. Additional buildings from either of the two organizations or community sites may be added in order to reach recruitment goals. These community sites will be identified through referrals from our CAB members. These include sites such as senior centers and other community sites (such as the Zeta and Waxter Senior Centers run by Baltimore City, Rhome and Co-op by Civic Works).where we coordinate directly with the directors and leadership of these centers. The study may also recruit participants and build partnerships through recruitment opportunities at community events. See Figure 1 for the overall study design.

Recruitment efforts will include posters, flyers, mailings, brochures, and information sessions at each site that will be led jointly by trained CHWs and the study team targeting residents who may be eligible as study participants and their communication partners. Following the information sessions, interested potential participants will undergo screening by the study staff after providing oral consent. Given the minimal risk involved with hearing screening, oral consent will be given to reduce the time burden on a potential participant in the screening process. Screening involves questions regarding demographics, self-reported perceived hearing handicap, and pure-tone audiometric threshold testing. Hearing screening will be conducted using a portable, remote audiometer specifically designed for field-testing without a soundproof booth. When interacting with potential participants, study staff will utilize an amplification device (such as the SuperEar or Pocketalker) to ensure individuals are able to hear the study staff. Potential participants who are eligible and interested in participating in the study will be asked to provide their contact information.

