We hypothesize that assignment to the immediate treatment group will have higher average HHIE scores at follow-up compared to those assigned to the delayed treatment group, who will not receive the intervention prior to the 3-month primary endpoint: a superiority hypothesis.

Effect Size	N per Arm	Total Sample Size	10% Attrition	20% Attrition
0.60	60	120	134	150
0.65	51	102	114	128
0.70	44	88	98	110
0.75	39	78	88	98
0.80	34	68	76	86
0.85	31	62	70	78
0.90	27	54	60	68

Table 1: Sample sizes necessary to achieve 90% power while maintaining a type I error rate at 0.05 using a two-sample t-test. These sample sizes are adjusted to account for potential loss to follow up.

A target sample size of 150 participants would ensure adequate power to test a clinically meaningful effect on the primary outcome, even with 20% attrition.

Framework: All hypotheses are being tested within a superiority framework. Individuals will be randomized to receive the intervention immediately (i.e. prior to the 3-month post-randomization visit, where the primary outcome is obtained), or to a wait-list control (i.e. receive the intervention after the primary outcome is obtained). For the primary outcome, it is hypothesized that individuals randomized to receive the intervention immediately will have greater declines in hearing handicap from baseline, as measured by the HHIE-S, than those assigned to the wait list control. Similarly, immediate treatment is hypothesized to be superior to wait list controls on all secondary outcomes.

Interim Analyses and Stopping Guidance: Given the short follow up window and minimal risk to participants, no interim analyses for efficacy or futility will be conducted. There is no anticipated need to stop the trial for safety concerns.

Timing of the Final Analysis: Data for the primary outcome will be considered complete after the last participant's last visit window for the primary outcome has closed. These records will be locked, although post-intervention follow-up data will continue to be collected. Efficacy of the intervention will be assessed only using information obtained at baseline and at the primary endpoint (3 months post-randomization). All data will be complete after the last participant's last window for the 12-month post-intervention visit has closed.

Timing of Outcome Assessments: A table of study visits and their corresponding visit windows is given in Table 2.

Study Visit	Immediate Treatment: Wave 1	Delayed Treatment: Wave 2

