The primary analysis will utilize the HHIE-S score obtained in-person whenever possible irrespective of study window and will use HHIE-S Scores obtained over the phone when an in-person visit was not obtained. Sensitivity analyses will include repeating the analysis with exclusion of outcomes obtained beyond 30 days outside of the study window: this will involve a new missing data indicator $R_i^S = 1$ if Y_{i1} is observed within the study window, and $R_i^S = 0$ otherwise.

Secondary Analyses: The secondary analyses will follow similarly from the primary analysis, using the same doubly robust estimator as described above. Secondary outcomes are listed in table 4: secondary outcome models will have the same specification for the outcome model (treatment indicator and linear terms for the baseline value of the outcome, age, and PTA) and the propensity score model (treatment indicator and linear terms for the baseline value of the outcome, age, and PTA).

Planned secondary analyses will be performed on the primary outcome, communication function as measured by HHIE-S, using the complier average causal effect (CACE) of the intervention, following a methodology similar to Stuart and Jo (2015). In this analysis, individuals are conceptualized as belonging to four latent classes, known as principal strata, which are unaffected by randomization. These strata include ‘compliers,’ who comply with whichever intervention assigned to them, ‘always takers,’ who will always take the treatment regardless of their treatment assignment, ‘never takers,’ who will never take

the treatment regardless of their treatment assignment, and ‘defiers,’ who will take whichever treatment they are not assigned. Adherence with the intervention will be defined as attending both scheduled intervention meetings and using the amplification device 1 or more hours per day at 3-months post-intervention. Since the HEARS intervention is not available outside of the study, we assume that there are no ‘always takers,’ and similarly, we assume that there are no ‘defiers.’

This analysis will be similar to the analysis described above, with an additional step added in creating the weights for the weighted regression. We will fit a logistic regression model for the probability of adherence or compliance, denoted A_i , among those in the immediate treatment group (wave 1):

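### The communication-partner criteria do not stop a waitlisted participant from attending another participant's HEARS sessions as a partner before their own primary outcome

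*Protocol*

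**What the plan says.** Protocol section 5 sets six inclusion criteria for a communication partner: age 18 or older, daily conversation with the participant, English-speaking, aural-oral communication, "Able to accompany participant to all intervention sessions & study team meetings", and able to follow instructions. The sole partner exclusion is "Individuals who do not fulfill inclusion criteria".

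Protocol section 4 (Participants) defines partners as "any individuals with whom the participant engages in daily spoken communication" and encourages each participant to involve a "communication partner willing to complete the program alongside them". Information sessions are described under Study Design as "targeting residents who may be eligible as study participants and their communication partners". Having a partner is optional.

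SAP section 3 randomizes participants 1:1, stratified by site so that the arms are balanced within buildings. It describes the delayed group as people "who will not receive the intervention prior to the 3-month primary endpoint". The delayed group's primary outcome may be collected up to 6 months after baseline (Protocol, Primary Outcome Data Collection Mode and Window).

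**The concern.** Suppose two people who talk every day, such as a couple or two neighbours, both meet the participant criteria. Each may enrol, each may name the other as partner, and they may be allocated to opposite arms. The waitlisted one can then attend all of the other's sessions. The first session covers hearing-loss education, communication strategies and amplification options; the second is device fitting and orientation (Protocol, Intervention Description).

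The primary contrast takes the delayed arm to be untreated at its assessment. HHIE-S is self-reported and the trial is open label, so educational content alone could lower a control's score and narrow the difference between arms. The overlap would also go unrecorded: the intervention-delivery deviations (Protocol section 8c; SAP section 4) cover non-receipt, incomplete delivery and delivery outside the window, but not early exposure of a control.

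**Working it through.** **1. Is the gap closed elsewhere?** No. Neither document bars a participant from being a partner, allocates couples or households together, or lists dual roles as a deviation.

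**2. What would an exposed control receive?** The intervention has three components: education, communication strategies and provision of an amplifier (Protocol section 4f; SAP section 3). A partner attending both sessions receives the first two and watches the fitting. The compensation table in Protocol section 10 lists the device and training materials for the participant and leaves the partner's cell blank. Exposure is therefore partial.

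**3. Reproducing the plan's figure.** Inputs from SAP sections 3 and 4: d = 0.60, two-sided alpha 0.05, 90% power, two-sample t-test, 1:1 allocation. The noncentral t gives 59.35, rounded up to 60 per arm, or 120 in total. With 20% attrition, 120 / 0.8 = 150. Both match SAP Table 1. Power at exactly 60 per arm is 90.3%.

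**4. Dilution.** Let f be the share of controls exposed and g the share of the full effect that each of them gains. The control mean moves by f × g of the effect, so

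d' = 0.60 × (1 − f × g).

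The documents give neither f nor g; both are assumptions. The 70 per arm comes from the 175 recruits in Protocol section 4 and the SAP's 20% attrition: 175 × 0.8 = 140, or 70 per arm.

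| f | g | d' | Power, 60 per arm | Power, 70 per arm |
|---|---|---|---|---|
| 0 | – | 0.60 | 90.3% | 94.1% |
| 5% | 0.5 | 0.60 × 0.975 = 0.585 | 88.8% | 93.0% |
| 10% | 0.5 | 0.60 × 0.95 = 0.57 | 87.2% | 91.8% |

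**5. How many pairs this implies.** If two people name each other and are allocated independently 1:1, about half of such pairs are split across arms, and each split pair yields one exposed control. Among 60 controls, f = 5% is 3 people, needing about 6 co-enrolled pairs (12 of 120 analysed, 10%). f = 10% is 6 people, needing about 12 pairs (24 of 120, 20%).

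**The case against.** The strongest reply is that the event may be rare and its effect small. Both members of a pair must be 60 or older, have a pure-tone average above 25 dB in both ears, meet the HHIE-S cut-off, use no device and have no ear disease needing evaluation. One must then name the other, and allocation must split them in the harmful direction. The documents do not say that this happened. Nor do they show that education without a device changes HHIE-S, so bias toward zero is plausible rather than established. With 175 recruited, both cases above keep more than 90% power. The primary model also adjusts for baseline HHIE-S, age and PTA, which the t-test calculation ignores. All of this stands and limits the point to a modest one. It does not close the gap in the criteria.

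Three stronger readings are tempting, and the documents do not support them.

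- **A reader might infer that the CACE analysis fails**, because SAP section 6 states "we assume that there are no ‘always takers". Adherence there requires attending both meetings and also using the device for at least an hour a day. A partner given no device does not meet that definition and is not an always taker.
- **A reader might assume that exposed controls gain the full effect (g = 1).** Without the amplifier, nothing in the documents supports that.
- **A reader might count someone who attends as a partner first and enrols later.** That exposure precedes randomization, so it is balanced between arms in expectation and is not contamination of the control arm.

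**Conclusion.** The point holds as an omission in the partner criteria. They permit a waitlisted participant, before the primary assessment, to attend an immediate-arm participant's sessions and receive the education and communication-strategy content without a device. The probable consequence is a modest bias of the primary contrast toward zero.

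Under the assumed 5% to 10% exposure at half benefit, the effect shrinks by 2.5% to 5%, and power at 60 per arm falls by 1.5 to 3.1 percentage points. At 70 per arm it stays above the 90% target. The overlap rate and the benefit are both assumptions. The study's own partner and participant records could settle the first.

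**What to change.** **Criteria.** Add one line to the partner exclusions in Protocol section 5: *Is a HEARS participant who has not yet completed the primary-outcome assessment.* The cost is that a few participants must attend without their preferred partner or name another one. The SAP's change log places every change after version 1.0 after unblinding of outcomes, so for this trial's primary comparison the line comes too late; it serves any further enrolment or reuse of the protocol.

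**Data already collected.**

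- Match the partner list against the participant list. Partners give written consent and complete questionnaires, so both lists should exist.
- Report dual-role people by arm as a protocol deviation. If there are none, one sentence saying so settles the matter.
- Keep the ITT analysis as primary.
- If exposed controls are found, add a sensitivity analysis, labelled as added after unblinding, that sets their missingness indicator to 0 and re-estimates the weights. SAP section 6 does the same for outcomes outside the study window. Simply dropping them would exclude people from one arm only, with nothing to account for the selection. The weighted version still assumes that, given arm, baseline HHIE-S, age and PTA, exposed controls resemble the rest of their arm, and this should be stated.

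The work is a record match and, at most, one further run of existing code.
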